2.3 Exploratory objectives

The exploratory objectives of the study are:

- To explore the profile in CRP and SAA over time
- To explore the PGA and Patient/ Parent’s global assessment of disease activity (PPGA) profiles over time
- To explore the Physician’s Severity Assessment of Disease Signs and Symptoms over time
- To explore the percentage of patients with the serologic remission defined as normalized SAA level in all patients who remain on randomized treatment or require blinded rescue over time
- To explore the percentage of patients who require blinded escape from Days 8 to 28
- To explore the number and duration of fever episodes by mean of patient diaries over time

- To explore the time to first new flare in responders in Epoch 2 switched to canakinumab every 8 weeks compared to placebo (Epoch 3)
- To evaluate the number of flares by patient and by Epoch
- To explore the use of rescue medication over time
- To explore percentage of patients who are able to reduce their corticosteroid maintenance dose at the end of each study epoch
- To explore the improvement in renal function and/ or proteinuria in patients with impaired renal function (eGFR <89 mL/min/1.73 m²) and/ or proteinuria at Baseline
- To explore the effect of the canakinumab-induced change of disease activity levels on aspects of Health-related Quality of Life. The following questionnaires will be used:
 - Auto-Inflammatory Disease Activity Index (AIDAI)
 - SF-12 Health Survey (SF-12) *to be completed by patients ≥18 years of age at Baseline*
 - Child Health Questionnaire – Parent Form 50 (CHQ-PF50) *to be completed by patients >5 - <18 years of age at Baseline*
 - Sheehan Disability Scale version 3 (SDS v3)
- To explore the relationships between disease-associated genetic mutations and drug response
- To explore the safety and efficacy of canakinumab in the non-randomized group of Japanese crFMF patients with non-exon 10 mutations, or patients >28 days but <2 years old entering the study in the open-label arm of Epoch 2, and in the roll-over TRAPS patients previously participating in clinical study CACZ885D2203 and/or the subsequent Multiple Patient Program (MPP) treatment plan CACZ885D2207M entering the study directly in the open-label arm of Epoch 3

3 Investigational plan

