3.1.2.2 Blinded escape (non-resolution/ early re-flare before Day 29)

The assignment to blinded escape will be managed by the IRT.

Patients whose index flare has not resolved by Day 15 will be eligible for blinded escape.

If patients experience persistent “mild”, “moderate” or “severe” disease activity (i.e., PGA ≥ 2 [clinical flare]), or CRP persistent >10 mg/L with less than 40% reduction from baseline from Day 8 to Day 14, they will also be eligible for blinded escape at an unscheduled visit.

In case one of the conditions described above occurs, patients will receive a single add-on s.c. injection of canakinumab (150 mg s.c. [or 2 mg/kg for patients ≤ 40 kg]) from Day 8 to Day 28 but will not be unblinded to their randomized treatment (see [Table 3-1](#)). This will lead to blinded up-titration to the next dosing regimen according to the initial randomized treatment and will be initiated from Day 29 onward through IRT.

- Patients randomized to canakinumab 150 mg q4w will receive 2 injections of canakinumab on Days 29, 57 and 85 equaling to a canakinumab 300 mg q4w regimen
- Patients randomized to placebo will receive 1 injection of canakinumab and 1 injection of placebo each on Days 29, 57 and 85 equaling to a canakinumab 150 mg q4w regimen

If the patient’s condition is not improving after add-on injection, rescue medication should be used from Day 15 until treatment is administered at Day 29. All patients on blinded escape will be followed-up for efficacy and safety.

Non-randomized cohort

Canakinumab naïve Japanese crFMF patients with non-exon 10 mutations or patients >28 days but <2 years old will initiate open-label treatment receiving canakinumab 150 mg (or 2 mg/kg for patients weighing ≤ 40 kg) q4w at Day 1. Index flare resolution will be assessed at Day 15.

Patients experiencing persistent “mild”, “moderate” or “severe” disease activity (i.e., PGA ≥ 2 [clinical flare]), or CRP persistent >10 mg/L with less than 40% reduction from baseline from Day 8 to Day 28 can receive a single add-on s.c. injection of canakinumab (150 mg s.c. [or 2 mg/kg for patients ≤ 40 kg]). If the patient’s condition is not improving after add-on injection, rescue medication should be used until the patient’s next visit at Day 29 when study treatment will be administered.

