Between-treatment differences for the proportion of patients with PGA < 2 at Week 16 will be analyzed using a logistic regression model with treatment group and baseline PGA as effect for each cohort. Patients needing dose escalation in the canakinumab arms, or who crossed-over from placebo arms to canakinumab in the randomized treatment epoch (Epoch 2), or discontinued from the study due to any reason prior to evaluating the endpoint at week 16 will be considered as having PGA ≥ 2 . In case of convergence issues then Firth's method will be used in the logistic regression model. If convergence issue is still not resolved then Canakinumab treatment group will be compared to placebo with respect to the proportion of patients with PGA < 2 at Week 16 will be analyzed using the Fisher's exact test.

Serological remission

Serological remission is defined as CRP ≤ 10 mg/L.

Between-treatment differences for the proportion of patients with CRP ≤ 10 mg/L at Week 16 will be analyzed using a logistic regression model with treatment group, and baseline CRP values (log(e) transformation) as effect for each cohort. Patients needing dose escalation in the canakinumab arms, or who crossed-over from placebo arms to canakinumab in the randomized treatment epoch (Epoch 2), or discontinued from the study due to any reason prior to evaluating the endpoint at week 16 will be considered as having CRP > 10 mg/L. In case of convergence issues then Firth's method will be used in the logistic regression model.

If convergence issue is still not resolved then Canakinumab treatment group will be compared to placebo with respect to the proportion of patients with CRP ≤ 10 mg/L at Week 16 will be analyzed using the Fisher's exact test.

Normalization of SAA

Normalization of SAA is defined as SAA ≤ 10 mg/L.

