SF-12 measurements consists of 12 questions over eight subscales (physical function, pain, general and mental health, vitality, social function, physical and emotional health). The subscales can be aggregated to derive a physical-component summary score (PCS) and a mental-component summary score (MCS).

The score will be summarized for each subscale and for PCS and MCS.

Child Health Questionnaire – Parent Form 50 (CHQ-PF50)

Descriptive statistics will be used to summarize patient responses on the CHQ-PF50[®] Questionnaire by epoch (2 and 3), analysis visit, initial randomized treatment and treatment sequence (as defined in [section 1.3](#)), total score (Physical (PhS) and Psychosocial

(PsS) scores) and by domain within each cohort. Only patients $>5 <18$ years of age at baseline are included.

Sheehan Disability Scale (SDS v3)

SDS score by domain and global functional impairment score will be summarized by epoch (2 and 3), analysis visit, initial randomized treatment and treatment sequence (as defined in [section 1.3](#)) within each cohort.

Number of flares

The number of new flares by patient will be summarized by epoch and treatment arms within each cohort.

Disease-associated genetic mutations

Relationships between disease-associated genetic mutations and CRP/SAA/PGA values at Day 15 on patients randomized to Canakinumab will be analyzed by cohort. T-test will be used for mean comparison between genetic mutations for CRP and SAA, and wilcoxon rank sum test will be used for mean comparison between genetic mutations for PGA. Mean CRP, SAA, PGA at Day 15 were compared between

For cr-FMF cohort

- (i) all M694V gene vs overall cr-FMF canakinumab treated patients
- (ii) all M694V gene vs non-M694V gene
- (iii) M694V heterozygous vs homozygous

For HIDS cohort

- (i) all V377I gene vs overall HIDS canakinumab treated patients
- (ii) all V377I gene vs non-V377I gene
- (iii) V377I heterozygous vs homozygous

For TRAPS cohort

- (i) all R92Q gene vs overall TRAPS canakinumab treated patients
- (ii) all R92Q gene vs non-R92Q gene
- (iii) R92Q heterozygous vs homozygous

In the T-test procedure, Pooled and Satterthwaite methods for the p-value were used depending on the test on equality of variances.

In the Npar1way procedure, p-value from Exact test was taken given the relatively small sample size of patients.

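### The mutation analysis compares untransformed Day 15 CRP and SAA by t-test without baseline, so it cannot separate genotype differences in pre-treatment inflammation from differences in response

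*SAP*

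**What the plan says.** Protocol 2.3 sets the exploratory objective: "To explore the relationships between disease-associated genetic mutations and drug response". SAP 1.10.5, under disease-associated genetic mutations, turns it into an analysis: "Relationships between disease-associated genetic mutations and CRP/SAA/PGA values at Day 15 on patients randomized to Canakinumab will be analyzed by cohort". For the two laboratory markers the method is: "T-test will be used for mean comparison between genetic mutations for CRP and SAA". The variant of the t-test is chosen by a variance test: "Pooled and Satterthwaite methods for the p-value were used depending on the test on equality of variances". PGA is compared by a Wilcoxon test, for which the "p-value from Exact test was taken given the relatively small sample size of patients".

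Each cohort has three comparisons: (i) carriers against the whole canakinumab group, (ii) carriers against non-carriers, (iii) heterozygous against homozygous. This point concerns (ii) and (iii). Comparison (i), for example "all M694V gene vs overall cr-FMF canakinumab treated patients", has a separate problem because one group contains the other.

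The section names no baseline covariate, change, ratio or transformation for CRP or SAA. It also has no rule for patients who received the early add-on injection.

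**The concern.** The objective is response to the drug; the outcome is where the patient ends up on Day 15. These differ when patients start at different levels. Entry requires CRP above 10 mg/L with no upper limit (Protocol 4.1.2 to 4.1.4), so starting values can vary widely. If carriers have a more intense index flare and fall by the same proportion as non-carriers, they are still higher on Day 15, and the test may be read as showing poorer response.

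The scale is a second issue. CRP and SAA are usually right-skewed. Choosing between pooled and Satterthwaite allows for unequal variances, not for skewness. The small-sample precaution taken for PGA is not taken for the laboratory markers in the same patients.

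Elsewhere the plan does use baseline. Resolution of the index flare can be met by a 70% fall from baseline (Protocol 6.4.4, SAP 1.10.1.1). The Week 16 CRP and SAA models include the baseline value, and the protocol's CRP model enters "baseline CRP values (log(e) transformation) as effect for each cohort". The CRP-reduction categories in SAP 1.10.5 do not fill the gap, because they are tabulated by randomized treatment and disease cohort, not by mutation.

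Treatment before Day 15 is not uniform either. Under Protocol 3.1.2.2, if early disease activity persists, "patients will receive a single add-on s.c. injection of canakinumab" from Day 8. The primary endpoint and its sensitivity analyses have rules for such patients (SAP 1.10.1.1 and 1.10.1.5); the mutation analysis has none.

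**Working it through.** **Inputs from the documents.** The plan gives no sample size, SD, effect size or alpha for this analysis, so it has no figure of its own to reproduce. The available number follows from Protocol 4: 180 randomized / (3 cohorts × 2 arms) = 30 canakinumab patients per cohort, then split by mutation. P-values are two-sided by default (SAP 1.1).

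**Assumed inputs, not in the documents.** Log-normal marker; baseline log SD 1.0; residual log SD 0.8; 15 versus 15 patients; two-sided 5%. Model: log(Day 15) = constant + b × log(baseline) + genotype effect + residual. The slope b is the carry-over from baseline to Day 15.

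**Step 1: what reaches Day 15.** With no genotype effect on response, a baseline ratio R gives a Day 15 geometric mean ratio of R^b. For R = 3 this is 3.0 at b = 1, 1.73 at b = 0.5 and 1.0 at b = 0. The log-scale correlation is b / √(b² + 0.8²): 1/√1.64 = 0.78 at b = 1, 0.5/√0.89 = 0.53 at b = 0.5, and 0 at b = 0.

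**Step 2: false positives.** Simulated with the SAP's rule (pooled or Satterthwaite after a variance test), no response difference:

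| Carry-over b | Raw t-test, 2-fold baseline difference | Raw t-test, 3-fold | Log ANCOVA |
|---|---|---|---|
| 1 | 14% | 32% | about 5% |
| 0.5 | 10% | 22% | about 5% |
| 0.25 | 6% | 10% | about 5% |
| 0 | 4% | 4% | about 5% |

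**Step 3: power.** Equal baselines and a true 2-fold difference at Day 15. The raw t-test has about 14% at b = 1, 33% at b = 0.5 and 42% at b = 0.3. A rerun for this note gave about 49% at b = 0. Log ANCOVA has about 61 to 63% throughout.

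**Step 4: wider ranges.** Log SD 1.0 or 1.5, correlation 0 to 0.7, splits 15/15, 20/10 and 10/20, 10,000 runs per setting:

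| Quantity | Raw t-test | Log ANCOVA |
|---|---|---|
| False positives, 3-fold baseline difference, correlation 0 | 2–5% | about 5% |
| Same, correlation 0.7 | 5–43% | about 5% |
| Power, true 2-fold difference | 4–37% | 20–71% |
| Power, true 3-fold difference | 9–68% | 43–98% |

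**Step 5: skewness alone.** With a 25/5 split and no difference in baseline or response, the raw t-test rejects in 9–11% of runs over the same log SD and correlation ranges, about twice the nominal level. Log ANCOVA stays near 5%.

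**The case against.** **The bias is conditional.** It needs baseline to differ by genotype and to predict the Day 15 level. The documents give neither figure, and with no carry-over there is no such bias. A reader might infer that the analysis will report pre-treatment inflammation as response. The text supports only that it cannot separate the two. This part of the objection stands.

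**The absolute level is part of the plan's own idea of response.** Resolution accepts CRP at or below 10 mg/L as an alternative to a 70% fall, and the SAP does not call a higher Day 15 level a poorer response. So it is too strong to say that the objective goes unanswered. But a difference between genotypes in the absolute level still cannot be attributed to the drug.

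**Low power is not only the t-test's doing.** At most 30 patients per cohort are split by mutation, and even the better model has only 20–71% power for a 2-fold difference. This stands as a limit on what any analysis can show.

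**ANCOVA is not a full cure.** Its 5% assumes baseline measured without error. If the single pre-dose value is a noisy reading of flare severity (assumed noise log SD 0.5 to 0.7 of a total of 1.0, full carry-over), it rejects in 11–25% of trials for a 3-fold difference, against 41–50% for the raw test. It is better, but not immune.

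**The plan's precedent is mixed.** The protocol logs baseline CRP, but its SAA model and both SAP models state no transformation. The case for logs rests on the likely shape of the data more than on consistency with the plan.

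**Conclusion.** The point holds as a limit on interpretation. As written, a significant mutation difference in CRP or SAA cannot be attributed to response, and a non-significant one says little. In the 15 versus 15 setting, the false-positive rate for a 3-fold baseline difference runs from about 4% to 32% depending on carry-over. Power for a true 2-fold difference is well below that of log ANCOVA when carry-over is strong, and closer to it when carry-over is weak. In a very unequal split, skewness alone takes the false-positive rate to about 10%. All of these figures rest on assumed log SDs, carry-over, group splits and fold differences.

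A reader might also infer that add-on dosing distorts the result materially. The share of patients given an add-on before Day 15 is not stated, so no size can be put on this; the gap is only that no rule is given.

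The analysis is exploratory, outside the H1 to H5 hierarchy (SAP 1.10.2.1) and has no stated alpha. Priority is low.

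**What to change.** In SAP 1.10.5, for comparisons (ii) and (iii), replace the t-test with a linear model for log Day 15 CRP, and another for log Day 15 SAA, with mutation group and log baseline of the same marker. Report the baseline-adjusted geometric mean ratio between genotypes with its confidence interval. Do not report an unadjusted ratio to baseline instead: if Day 15 does not depend on baseline, a test of that ratio differs by genotype in about 29% (2-fold baseline difference) to 62% (3-fold) of trials with no genotype effect at Day 15.

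Show patients given an add-on injection before Day 15 separately, or repeat the analysis without them. Do not substitute the last value before the add-on. The visit columns of Protocol Table 6-1 go straight from Day 1 to Day 15, and Protocol 6.4.3 provides for CRP at unscheduled visits but does not say so for SAA, so for SAA that value may be the baseline itself.

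Cost: some SAP wording and one model per marker and comparison, using Day 15 and baseline values already planned. One detail needs a rule: under the standardization formula in SAP 1.10.1.1, a CRP at the laboratory's lower limit becomes 10 × 0 = 0, which has no logarithm, so the handling of values at or near zero must be stated. Trial conduct and the primary analysis do not change.

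### SAP 1.10.5 tests mutation carriers against the whole canakinumab group that contains them, using tests for separate groups; the p-values of comparison (i) are invalid in all three cohorts (minor, exploratory)

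*SAP*

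**What the plan says.** SAP 1.10.5, under disease-associated genetic mutations, relates genotype to CRP, SAA and PGA. The population is fixed by the words "values at Day 15 on patients randomized to Canakinumab will be analyzed by cohort". Each cohort has three comparisons:

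- (i) carriers against the overall group: "all M694V gene vs overall cr-FMF canakinumab treated patients", "all V377I gene vs overall HIDS canakinumab treated patients" and "all R92Q gene vs overall TRAPS canakinumab treated patients".
- (ii) carriers against non-carriers, for example "all M694V gene vs non-M694V gene".
- (iii) heterozygous against homozygous patients.

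One method covers all three. For the two markers, "T-test will be used for mean comparison between genetic mutations for CRP and SAA", with the variant chosen by a variance test: "Pooled and Satterthwaite methods for the p-value were used depending on the test on equality of variances". For PGA, "wilcoxon rank sum test will be used for mean comparison between genetic mutations for PGA", with an exact p-value. The section does not remove carriers from the overall group, adjust for the overlap, or mark (i) as descriptive.

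**The concern.** A pooled or Satterthwaite t-test and a rank-sum test treat their two groups as independent samples with no patient in common. In (i), each carrier contributes to both sides, so the two means are positively correlated and the standard error of their difference is computed as if they were not. The exact rank-sum p-value fails for the same reason: its reference distribution allocates distinct patients to two groups, whereas here each carrier's score is entered twice.

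Three outcomes in three cohorts give nine such p-values. Relating genotype to drug response is a stated exploratory objective (Protocol 2.3). The practical risk is a report in which (i) shows no association and (ii) shows one, for the same mutation, outcome and patients.

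**Working it through.** The documents state no sample size, power, significance level or carrier count for this analysis, so there is no planned figure to reproduce.

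**Inputs**
- N = 30 canakinumab patients per cohort, the planned arm size (Protocol section 4).
- Two-sided p-values, the default in SAP 1.1.
- Assumed: 5% level, normal data with equal variance s², and carrier share f = m/N, where m is the number of carriers, over a range.

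**Standard error.** The two-sample test assumes a variance for the difference of s²(1/m + 1/N). Because the carriers are part of the N, the covariance of the two means is s²/N, and the true variance is s²(1/m + 1/N − 2/N) = s²(1/m − 1/N). Hence true SE / assumed SE = √[(1 − f)/(1 + f)].

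- m = 9 (30%): (0.1111 − 0.0333)/(0.1111 + 0.0333) = 0.538; square root 0.73.
- m = 15 (50%): (0.0667 − 0.0333)/(0.0667 + 0.0333) = 0.333; square root 0.58.
- m = 24 (80%): (0.0417 − 0.0333)/(0.0417 + 0.0333) = 0.111; square root 0.33.

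**Relation to (ii).** If every patient is either a carrier or a non-carrier, the overall mean is f × carrier mean + (1 − f) × non-carrier mean. Then carrier mean − overall mean = (1 − f) × (carrier mean − non-carrier mean). Comparison (i) is (ii) shrunk by a known factor, with the same sign.

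The rank-sum statistic behaves alike. Carriers compared with themselves add exactly m²/2 to the Mann-Whitney count (ties counted as half). The centred statistic is therefore the same in (i) and (ii), and only the reference distribution is wrong.

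**Pooled t-test, simulated, N = 30, nominal two-sided 5%** (power is for an assumed difference of 1 SD between carriers and non-carriers):

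| Carrier share | Type I error of (i) | Power of (i) | Power of (ii) |
|---|---|---|---|
| 10% | about 2% | – | – |
| 30% | about 0.5% | 32% | 68% |
| 50% | under 0.1% | 13% | 75% |
| 80% | about 0% | 0% | 56% |

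The error rate of (ii) stays near 5%. At a 1-SD difference, (ii) is significant and (i) is not in about 36%, 62% and 56% of runs at shares of 30%, 50% and 80%. The reverse did not occur.

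**Other planned tests.** The Satterthwaite form is less conservative. Its type I error is 3.5% at 5 of 30 carriers, against 1.6% for pooled, and about 6% at 3 of 30. For the rank-sum test on an assumed five-level score (normal approximation, not the exact p-value), it is 1.4%, 0.3% and 0.02% at 5, 10 and 15 of 30.

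**The case against.** The strongest case on the other side concerns consequence, and much of it stands.

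- **Comparison (i) is not always blind.** A reader might infer that it will report no difference almost whatever the truth. That holds only when carriers are a large majority. At a 30% share and an assumed 1.5-SD difference, the pooled test in (i) still has about 75% power; at 2 SD it has about 97%.
- **The objective survives.** A reader might also infer that the genotype question becomes uninterpretable. It does not: (ii) and (iii) use separate groups and answer it, and (i) and (ii) can differ in significance but not in direction.
- **The error is not always conservative.** The Satterthwaite version slightly exceeds 5% when carriers are very few.
- **The shrinkage identity is conditional.** HIDS entry accepts a genetic or an enzymatic diagnosis (Protocol 4.1.3), and SAP 1.5 tabulates confirmed mutation as no or yes. Patients without an identified genotype could be in the overall HIDS group, and 1.10.5 does not say whether they count as non-V377I. One cannot therefore say without qualification that (i) carries nothing beyond (ii).
- **The analysis may already have been run.** The section mixes future and past tense. If so, deleting (i) would remove a performed analysis from the record, and descriptive reporting is safer.

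None of this makes the p-values of (i) correct. Exploratory status excuses low power and unadjusted multiplicity. It does not excuse a test whose independence assumption is broken by construction. Nor can the overall group be read as the remaining patients, because (ii) is already that comparison.

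**Conclusion.** The point holds as a minor technical correction. As written, the p-values of (i) are invalid in all three cohorts because the groups overlap. Over most of the plausible range they are too large, so the usual result is a missed association that (ii) would show. That the p-values are invalid needs no numerical assumption. Its size depends on the assumed carrier share, 5% level, normal data, equal variances, effect size and the planned 30 patients with a Day 15 value.

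The analysis is exploratory and has no part in the H1 to H5 sequence of SAP 1.10.2.1. No primary, secondary or safety conclusion depends on it.

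**What to change.** In SAP 1.10.5, for all three cohorts:

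1. Remove the significance test from comparison (i) and show the overall canakinumab mean for the cohort descriptively beside the carrier mean.
2. State that inference on genotype rests on (ii), carriers against non-carriers, and (iii), heterozygous against homozygous.
3. State how patients without an identified genotype, who are possible in HIDS, are classed in (ii): as non-carriers, as a separate group, or excluded.

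This changes three comparison lines and adds two sentences. It needs no new data and does not touch the confirmatory analyses. If p-values for (i) already exist, keep the means and note that the test was dropped because the groups overlap.

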The study population will consist of male and female patients >28 days and confirmed TRAPS (cohort 1), HIDS (cohort 2), or crFMF (cohort 3).

It is aimed to randomize a total of 180 patients (60 per cohort, 30 per treatment arm) in approximately >20 centers worldwide. Since a 20% screening failure rate is expected, it is estimated that approximately 225 patients have to be screened.

The following patient populations will be screened at Day 1 and directly entered into the open-label treatment arm of the randomized withdrawal epoch (Epoch 3) at Day 113:

- TRAPS patients previously participating in clinical study CACZ885D2203 or the subsequent MPP treatment plan CACZ885D2207M (at most 19 patients).

In addition, the following patient populations will be screened and will enter into the open-label treatment arm of the Epoch 2 at Day 1:

- Male and female patients >28 days but <2 years old with bodyweight ≥ 3.75 kg
- Approximately 5 Japanese crFMF patients with non-exon 10 mutations otherwise fulfilling all the mandatory inclusion and exclusion criteria.

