- a. A screening epoch to assess patients' eligibility of up to 12 weeks duration (Epoch 1)
- b. An open-label epoch of 16 weeks (Epoch 2)
- c. An open-label epoch of 24 weeks (Epoch 3)

- d. An open-label treatment epoch of 72 weeks to collect long-term safety data for canakinumab (Epoch 4)

All data will be analyzed separately for each independent cohort (TRAPS, HIDS, crFMF).

The purpose of the study is to provide evidence supporting answers to following questions. The data will be analyzed by Epoch:

1. Whether canakinumab at a starting dose of 150mg s.c. (or 2mg/kg for patients ≤ 40 kg) administered every 4 weeks is able to induce and maintain a clinically meaningful reduction of disease activity defined as resolution of the index flare at Day 15 and no new disease flares over 16 weeks of treatment in a greater proportion of patients with TRAPS, HIDS, or crFMF compared to placebo (Data from Epoch 2)
2. Whether, in patients responding to the initial dosing regimen of every 4 weeks, canakinumab will maintain its clinical efficacy if administered at a reduced dosing interval of 150mg s.c. (or 2mg/kg for patients ≤ 40 kg) every 8 weeks. (Data from epoch 3 and 4)

Safety data for the subgroup of patients coming from ACZ885D2203 and/or the subsequent Multiple Patient Program (MPP) treatment plan CACZ885D2207M collected in Epoch 3 and 4 will separately be reported from the other patients who will be screened and randomized in Epoch 2.

Safety data for the subgroup of canakinumab naïve Japanese crFMF patients with non-exon 10 mutations, and patients >28 days but <2 years old, collected in Epoch 2, 3 and 4 will separately be reported from the other patients who will be screened and randomized in Epoch 2.

Summary statistics for continuous variables will include N, mean, standard deviation, minimum, lower quartile, median, upper quartile, maximum, and number of patients with non-missing data (n). Summary statistics for discrete variables will be presented in contingency tables and will include absolute and relative frequencies.

If not otherwise specified, p-values will be presented as two-sided p-values and two-sided confidence intervals will be displayed.

All listings will be presented by cohort and treatment sequence.

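### The genotype t-tests for Day 15 CRP and SAA let a weak variance pre-test choose the p-value and state no transformation; fixing one unequal-variance test on the log scale removes a possible error inflation in small subgroups

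*SAP*

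**What the plan says.** The part of SAP 1.10.5 on disease-associated genetic mutations sets out the analysis as follows.

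- Population: "CRP/SAA/PGA values at Day 15 on patients randomized to Canakinumab will be analyzed by cohort".
- Test for the two markers: "T-test will be used for mean comparison between genetic mutations for CRP and SAA". No transformation is mentioned.
- Choice of p-value: "In the T-test procedure, Pooled and Satterthwaite methods for the p-value were used depending on the test on equality of variances". The variance test and its level are not named.
- Comparisons: three per cohort, for example "all R92Q gene vs non-R92Q gene" and "R92Q heterozygous vs homozygous". Expected subgroup sizes are not given.
- For PGA, which gets a Wilcoxon test, the plan takes account of size: "p-value from Exact test was taken given the relatively small sample size of patients". Nothing comparable is said for the t-tests.

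The ceiling on numbers comes from Protocol Section 4 (Population): "It is aimed to randomize a total of 180 patients (60 per cohort, 30 per treatment arm"). Sidedness follows the default in SAP 1.1: "If not otherwise specified, p-values will be presented as two-sided p-values and two-sided confidence intervals will be displayed". No significance level is set for the genetic tests.

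Protocol 9.5.1 applies a natural-log transformation to baseline CRP in the logistic model for serological remission, so the log scale is not foreign to this plan.

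**The concern.** Under this rule a non-significant variance test leads to the pooled p-value. Non-significance is weak evidence of equal variances when one group has only a handful of patients. The pooled test goes wrong when group sizes and variances are both unequal, and the pre-test is least able to detect that situation when a group is small. If the rarer genotype is the more variable one, chance differences are reported as genotype effects too often. If it is the less variable one, real differences become harder to see.

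Scale matters as well. The protocol's own use of a log for baseline CRP suggests skewness, and a t-test on raw skewed values in very unequal groups has problems that neither version of the test solves.

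The rule governs 3 cohorts x 3 comparisons x 2 markers = 18 t-tests. The first comparison in each cohort sets carriers against a group that contains them, which is a separate problem. The other 3 x 2 x 2 = 12 are directly affected.

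**Working it through.** The documents give no error rate, power, subgroup size or SD for these tests, so there is no plan figure to reproduce.

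**Inputs from the documents:** n1 + n2 at most 30 (Protocol Section 4); two-sided p-values (SAP 1.1); the pooled/Satterthwaite choice (SAP 1.10.5).

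**Assumptions:** smaller group of 3 to 15 out of 30; SD ratio (smaller/larger group) 0.5 to 3; equal true means; pre-test is a two-sided F test at 5%; t-tests at 5%.

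**Formulas**
- Pre-test: F = s1²/s2².
- Pooled variance of the difference: sp²(1/n1 + 1/n2), with sp² = [(n1−1)s1² + (n2−1)s2²]/(n1+n2−2).
- Satterthwaite: s1²/n1 + s2²/n2, with approximated degrees of freedom.

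**Direction, by hand (expected values)**
- 3 vs 27, SDs 2 and 1. True variance: 4/3 + 1/27 = 1.370. Pooled: (2×4 + 26×1)/28 = 1.214, times (1/3 + 1/27) = 0.370, gives 0.450. That is about one third of the truth, so the pooled test rejects too often.
- 3 vs 27, SDs 0.5 and 1. True: 0.25/3 + 1/27 = 0.120. Pooled: (2×0.25 + 26)/28 × 0.370 = 0.351. That is about 2.9 times the truth, so the test is conservative.
- 15 vs 15, SDs 2 and 1. True: 4/15 + 1/15 = 0.333. Pooled: 2.5 × 2/15 = 0.333. No distortion.

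**Simulation, normal data, smaller group with twice the SD** (300,000 trials per row)

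| Groups | Pre-test misses | Two-step error | Pooled error when pre-test is non-significant | Satterthwaite always |
|---|---|---|---|---|
| 3 vs 27 | 64% | 17.9% | 27.4% | 6.9% |
| 4 vs 26 | 55% | 14.5% | 25.7% | 5.9% |
| 5 vs 25 | 49% | 11.9% | 23.6% | 5.6% |
| 6 vs 24 | 44% | 10.4% | 22.2% | 5.4% |
| 8 vs 22 | 36% | 8.0% | 18.5% | 5.2% |

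Nearly all the excess comes from trials that pass the pre-test: at 3 vs 27, 0.635 × 0.274 = 0.174 of the 0.179.

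**Other normal-data settings, two-step error**
- SD ratio 1.5: 13.7% (3 vs 27) down to 8.3% (8 vs 22), with the difference missed in 71-82%.
- SD ratio 3: 16.9% (3 vs 27) down to 7.3% (6 vs 24), missed in about 12-37%.
- 10 vs 20, SD ratio 2: 6.7%. 15 vs 15: about 5%.
- Smaller group with half the SD, 3 to 6 of 30: 2.3-3.1%.
- Pre-test at 10% instead of 5%, SD ratio 2, 3 to 6 of 30: 8.8-16.1%.

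**Skewed data left untransformed** (lognormal, log-SD 0.9 assumed, equal raw means, 100,000 trials; Satterthwaite always / two-step rule)

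| SD ratio | 3 vs 27 | 6 vs 24 |
|---|---|---|
| 1 | 14.8% / 8.6% | 8.3% / 7.7% |
| 1.5 | 17.7% / 9.0% | 12.5% / 9.6% |
| 2 | 17.8% / 14.7% | 14.2% / 13.9% |
| 3 | 17.0% / 25.3% | 15.3% / 18.6% |

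On raw skewed values neither rule holds 5%, and up to an SD ratio of 2 Satterthwaite alone is the worse of the two. After a log transformation lognormal data are normal, so the normal-data results apply, with the SD ratio read on the log scale.

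**The case against.** The strongest objection is that simply replacing the two-step rule by Satterthwaite could make matters worse. CRP and SAA are plausibly skewed, and the last table shows higher error for Satterthwaite at 3 vs 27 with equal SDs (14.8% against 8.6%). This stands, and it is why the change of scale belongs with the removal of the pre-test. Even with normal data, Satterthwaite runs at about 6-8% when one group has 3 patients.

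A second objection is that the figures come from an unfavourable corner: a very small group that is also the more variable one. That also stands. The documents give no genotype frequencies or SDs, so nobody can say from them which case applies.

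A third is that the tests are exploratory, with no allocated alpha and no multiplicity control, so there is no 5% guarantee to break. This limits the consequence, but these p-values will still be read as evidence on genotype and response, a listed exploratory objective in Protocol 2.3.

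A reader might infer that the pre-test usually misses a real variance difference. The calculations do not support that in general: at SD ratio 2 a clear majority is missed only with 3 or 4 patients in the small group, and with 6 the figure is 44%.

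**Conclusion.** The rule is weak for this setting and worth changing. At an assumed two-sided 5% level, with normal data and a smaller group of 3 to 6 out of 30 having twice the SD, its error is about 18% down to 10%. With balanced groups it is about 5%, and with a less variable small group 2-3%. Subgroup sizes, SDs, the variance test and both levels are assumptions, because the plan states none of them.

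It would be tempting to conclude that the genetic p-values are generally inflated to 10-18%, or that the trial's findings are at risk. The documents support neither. The inflation is conditional, and the analysis stands apart from the primary endpoint and the H1-H5 hierarchy in SAP 1.10.2.1. This is a minor improvement to an exploratory analysis.

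**What to change.** In SAP 1.10.5, delete the sentence that makes the p-value depend on a variance test and replace it with: *CRP and SAA will be compared on the log scale using the Satterthwaite (unequal-variance) p-value and 95% CI for all t-tests.*

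Add a rule, set before the data are seen, for values that have no logarithm. The CRP standardisation in SAP 1.10.1.1 returns 0 when a result equals the laboratory's lower limit, so zeros can occur if standardised CRP is analysed.

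The two parts must go together; Satterthwaite on untransformed CRP or SAA is not recommended. Where a group has only about 3 patients, the p-value should be read with caution or replaced by an exact or permutation test.

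Cost: a sentence or two of SAP text and no new data. Power is slightly lower when variances really are equal, and results become ratios of geometric means instead of differences in means. The change does not repair the first comparison in each cohort, whose groups overlap.
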